### 9.1 Objectives

The primary objectives of this phase II study are: 1) to examine the **feasibility** of a prospective multi-institutional study of TOS followed by risk-adjusted adjuvant therapy in this patient population; and 2) to assess the oncologic **efficacy** of the proposed treatment strategy (TOS + reduce dose radiotherapy) for the intermediate risk group. The accrual rate, patient risk distribution (especially the proportion of the intermediate risk group), and surgical quality are used to evaluate feasibility of the study. The 2-year progression-free survival (PFS) rate will be used to evaluate the efficacy in the intermediate risk group. The table below gives a summary of the stopping rules / decision rules to be implemented with regard to these two primary objectives. Details are given in following sections.

Rev. 2/15

Objective	Endpoint	Assessment Time point	Suspension rules / Decision Rules
Efficacy	1-year PFS rate	First 10 patients in arm A followed for 1 year	Currently enrolled and subsequent patients who have not progressed will receive radiotherapy 50 Gy if 2 or more patients progress or die within 1 year
	1-year PFS rate	First 10 patients with p N2C/N3 disease followed for 1 year	Currently enrolled and subsequent patients with p N2C/N3 disease who have not progressed will receive IMRT 66 Gy + cisplatin (Arm D treatment) if 2 or more patients progress or die within 1 year
	1-year PFS rate	First 40 patients in each of arms B and C followed for 1 year	Suspend trial and review if $\geq 6$ patients (per arm) progress or die within 1 year
	2-year PFS rate	End of study	Treatment worthy of further study if higher limit of the 90% CI $> 85\%$
Feasibility	Accrual	13-18 months post-activation	Accrual will be monitored by DSMC and NCI (see section below)
	Risk distribution	First 59 patients evaluated for risk	Suspend trial and review if $\leq 21$ patients with intermediate risk
	Surgical quality	First 59 patients completed transoral resection and have CTCAE forms submitted	Suspend trial and review if $\geq 13$ patients reported with grade 3-4 bleeding or positive margins

Secondary objectives include assessing quality of life (QOL) and swallowing function before and after treatment, evaluating toxicity, and investigating the prognostic effects of various biomarkers (details follow).

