## 9.3 Primary Objective: Efficacy

### *Primary Endpoint—2-year PFS rate*

The sample size calculations are based on the efficacy endpoint of 2-year PFS rate, which is defined as the proportion of patients alive and progression-free at 24 months measured from date of registration onto Step 1. Patients who die without disease progression within 24 months and patients who begin non-protocol therapy without evidence of progression within 24 months will not be considered to be progression-free at 24 months. The 2-year failure proportions that include second primary cancers from the head and neck region as event will also be reported.

The regimen of TOS + low-dose radiation (Arm B and Arm C, separately) may be considered worthy of further study if the true 2-year PFS rate is close to 85% (the observed rate among high-dose radiation patients in E2399).

Assuming 90 analyzable patients per arm for the intermediate group, the following table displays the exact 90% binomial confidence intervals (CIs) for the 2-year PFS rate for each of Arm B and C, assuming various observed 2-year

Rev. 6/14

PFS rate. For example, if 79 out of 90 analyzable patients per arm are alive and progression free at 2 years, the 90% confidence interval will be 81% to 93% with a width of 12%. This study will need 180 analyzable patients in total for the two randomized arms (Arms B + Arm C).

	Number of Alive and Progression Free at 2 Years			
	71	75	79	83
90% CI	(0.71, 0.86)	(0.76, 0.89)	(0.81, 0.93)	(0.86, 0.96)

With regard to p16 status, while central evaluation of pathology reports will be conducted retrospectively, actual assays will not be run or reviewed centrally. Patients who drop-out prior to radiation therapy due to any reason will also be excluded from the primary analysis .

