In the original design, the risk distribution was assumed to be 10% low risk, 60% intermediate risk, and 30% high risk, and an interim analysis for the first 59 patients who complete transoral resection was scheduled. Based on the analysis results, among the 104 evaluable patients (not ineligible based on current evaluation, and started treatment on step 2), the estimated risk distribution is: 8% low risk, 48% intermediate risk and 32% high risk (13 (12%) patients had potentially misclassified risk category/ arm based on their surgical data and the study team is taking various actions trying to improve this). As was stated in the original design, in case the proportion of the intermediate risk patients is off over 5% from the anticipated 60%, the accrual goal would be adjusted, With this new accrual goal, we expect at the end of the study ~180 evaluable patients would be intermediate risk, ~120 high risk, and ~30 low risk.

In analyzing the 2-year PFS rate, 90% exact binomial confidence intervals will be computed for each arm. Only eligible patients with confirmed P16+ status who started radiotherapy will be analyzed (by arm). The regimen will be considered worthy of further study if the higher limit of the computed 90% CI exceeds 85%.

Comparisons of 2-year PFS rates between Arms B and C, Arms B and D, and Arms C and D are exploratory endpoints. Since one of the randomized arms proposed in this study is likely to be selected for a follow-up phase III study, the exploratory comparison of 2-year PFS rate between the two randomized arms is more important and a p-value  $\leq 0.05$  will be considered statistically significant. For the other two comparisons (Arms B and D; Arms C and D), the Type I error rate of 5% will be divided by the two tests (i.e., 0.05/2 considered statistically significant). Therefore, the family-wise error rate of 0.10 will be protected for the multiple comparisons in the 2-year PFS rate among arms. Power for various differences in the 2-year PFS rate is shown below, assuming a two-sided Fisher's exact test and 90 analyzable patients in Arms B or C, and 120 analyzable patients in arm D.

Difference in 2-year PFS rate between arms	Arm C vs. Arm B	Arm B (or C) vs. Arm D
10% (85% vs. 75%)	0.32	0.27
15% (85% vs. 70%)	0.62	0.58
20% (85% vs. 65%)	0.85	0.83
25% (85% vs. 60%)	0.96	0.96

*Interim Analysis—1-year PFS rate*

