To safeguard against an unacceptably high failure rate for Arm B and Arm C, in which both the radiation dose is reduced and chemotherapy is removed, an interim look at 1-year PFS rate will be performed for the first 40 eligible and treated patients in Arm B and Arm C, separately. It is expected, for either arm, 90% of patients will be alive and progression free at 1 year (Fakhry, C, JNCI, 2008). The event rate will be deemed too high if 6 or more such events are observed within 1 year, which corresponds to an empirical progression rate of 15%. In this case, the trial will be suspended and a panel review will be called. The following table summarizes the probability of suspending the trial under various true 1-year progression rates in Arm B (and Arm C). For instance, the probability of suspending the trial is at least 84% if the true 1-year progression rate is 20% or higher. The study will continue accrual while we are waiting for the decision from this interim analysis.

True 1-yr progression rate for patients with intermediate risk	0.10	0.15	0.20	0.25	0.30
Probability of suspending the trial	0.21	0.57	0.84	0.96	0.99

Similarly, to safeguard against an unacceptably high failure rate for the observational Arm A, an interim look at 1-year PFS rate will also be performed for the first 10 eligible and treated patients (a total of 38 patients is expected to be accrued to this arm). Among these 10 patients, if 2 or more patients progressed or died within 1 year, currently enrolled and subsequently enrolled low risk patients who have not progressed will be directly assigned to radiotherapy IMRT 50 Gy. The same interim monitoring rule will be applied to the patients with pathological N2C/N3 disease who are directly assigned to Arm C (expected to be 5% of the total population). That is, if 2 or more patients among the first 10 such patients progress or die within the first year, currently and subsequently enrolled patients with p N2C/N3 disease will be treated with IMRT 66 Gy + cisplatin (Arm D treatment). The following table summarizes the probability of observing 2 or more events, under various true 1-year PFS rate for this group of patients.

True 1-yr PFS rate	0.10	0.15	0.20	0.25	0.30
Probability of observing 2 or more events	0.26	0.46	0.62	0.76	0.85

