### 12.1 Diagnostic Review and Classification (MANDATORY)

Original diagnostic and surgical pathology materials (tissue and reports) will be retrospectively reviewed by [name] at Mayo Clinic Rochester. The results of the evaluations will not be reported to the sites and will not impact patient participation in the trial, but will be used to determine the evaluability of patient data in the analysis of the clinical data.

Surgical materials will be evaluated for:

- A. Perineural Invasion, surgical: Reported as absent or present
- B. Lymphovascular Invasion, surgical: Reported as absent or present
- C. Extracapsular Extension, surgical: The absence or presence of ECE should be documented in the final surgical pathology report in the following manner:
  - absent (nodal metastasis with smooth/rounded leading edge confined to thickened capsule/pseudocapsule),
  - present - minimal (tumor extends  $\leq 1$  mm beyond the lymph node capsule), or
  - present - beyond minimal (gross, tumor extends  $> 1$  mm beyond the lymph node capsule (includes soft tissue metastasis)

The p16 status and reporting from the original diagnostic assessments will be also be reviewed to confirm patient evaluability. p16 immunohistochemistry must have been performed in a CLIA laboratory. Positivity is defined by strong cytoplasmic immunoreactivity noted in  $\geq 70\%$  of tumor cells.

Data from the preoperative CT/MRI scans analyzed for nodal stage and prediction of ECE will be correlated with final pathologic nodal stage, presence and extent of ECE ( $\leq$  or  $> 1$ mm).

Rev. 1/16

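### Is the end-of-study rule for 2-year PFS too easy to pass because it uses the upper confidence limit and names no unacceptable rate?

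*Combined protocol and SAP*

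**What the plan says.** Section 9.3 says the low-dose regimen, judged separately for Arms B and C, "may be considered worthy of further study if the true 2-year PFS rate is close to 85" per cent, the rate seen with high-dose radiation in E2399. For the analysis, "90% exact binomial confidence intervals will be computed for each arm", and "The regimen will be considered worthy of further study if the higher limit of the computed 90% CI exceeds 85" per cent. The decision table in Section 9.1 has the same rule: "Treatment worthy of further study if higher limit of the 90% CI" is above 85%.

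The size is justified by precision. "Assuming 90 analyzable patients per arm for the intermediate group", Section 9.3 tabulates exact 90% intervals for 71, 75, 79 and 83 patients alive and progression-free at 2 years. No pass probabilities accompany the final rule. They are printed for the 1-year interim look, under which "The event rate will be deemed too high if 6 or more such events are observed within 1 year" among the first 40 patients of an arm, leading to suspension and a panel review.

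On the analysis set, "Patients who drop-out prior to radiation therapy due to any reason will also be excluded from the primary analysis", and Section 12.1 says the results of retrospective pathology review "will be used to determine the evaluability of patient data in the analysis of the clinical data". The opening text of Section 9 defines evaluable patients as those who are eligible and started step 2 treatment, and it raises accrual to 515 so that 180 such intermediate-risk patients remain.

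**The concern.** A phase II efficacy rule usually asks the data to rule out a poor result. This one asks only that they fail to rule out a good one. With no unacceptable rate and no pass probabilities, a reader cannot see directly how often a poor regimen would be carried forward. This is the only formal end-of-study decision on the primary efficacy endpoint, and both arms de-escalate treatment, so wrongly passing an arm matters.

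The rule also responds to sample size in an unwelcome direction. A smaller analysis set gives a wider interval and a higher upper limit, so substantial loss of patients weakens the screen where it would normally cost power. The exclusions in Sections 9.3 and 12.1 seem to open the way to such loss.

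**Working it through.** **Inputs.** 90 analysable patients per arm, two-sided exact (Clopper-Pearson) 90% interval with 5% in each tail, and a threshold of 85% (all Section 9.3); the 6-of-40 interim rule (Section 9.3, interim analysis); 515 accrued, 73% evaluable, 48% of those intermediate risk (Section 9 opening text and 9.2).

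**1. The plan's own figures.** For x successes in n, the lower limit is the 5% quantile of Beta(x, n−x+1) and the upper limit is the 95% quantile of Beta(x+1, n−x). With n = 90:

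| x | Computed | Plan |
|---|---|---|
| 71 | 0.706 to 0.857 | 0.71, 0.86 |
| 75 | 0.755 to 0.894 | 0.76, 0.89 |
| 79 | 0.806 to 0.930 | 0.81, 0.93 |
| 83 | 0.859 to 0.963 | 0.86, 0.96 |

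All agree after rounding. The interim table also reproduces: P(6 or more of 40) = 0.206, 0.567, 0.839, 0.957 and 0.991 at 1-year progression rates of 10, 15, 20, 25 and 30%.

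**2. The cut-off.** At 70/90 the upper limit is 0.848 (fail); at 71/90 it is 0.857 (pass). The smallest passing result is 71/90 = 78.9%, which is the first column of the plan's table.

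**3. Pass probabilities at n = 90.** P(X ≥ 71), X binomial(90, p):

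| True 2-year PFS | 70% | 75% | 80% | 85% |
|---|---|---|---|---|
| P(pass) | 0.039 | 0.236 | 0.662 | 0.957 |

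**4. A lower-limit rule for comparison.** Assume a floor of 70% (the documents give none) and require the lower 90% limit to exceed it. At 70/90 the lower limit is 0.694 (fail) and at 71/90 it is 0.706 (pass). Cut-off and pass probabilities are the same as in step 3. At n = 100 the lower-limit rule needs 78 and passes a true 70% arm with probability 0.048; the plan's rule needs 79 and gives 0.029. Above the planned size the replacement can be the laxer of the two. With an assumed 75% floor the cut-off is 75/90, with pass probability 0.040 at a true 75% but only 0.730 at a true 85%.

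**5. Dependence on n under the plan's rule, true rate 70%.**

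| n | 90 | 85 | 80 | 78 | 76 | 75 | 74 | 60 |
|---|---|---|---|---|---|---|---|---|
| Cut-off | 71 | 67 | 63 | 61 | 59 | 58 | 58 | 46 |
| P(pass) | 0.039 | 0.045 | 0.053 | 0.069 | 0.090 | 0.102 | 0.071 | 0.162 |

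Over n = 80 to 90 the range is 0.039 to 0.077. The path is a saw-tooth, and n = 75 is a local peak.

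**6. How far n could fall.** 180/0.35 = 514.3, hence 515; and 515 × 0.73 × 0.48 = 180.5, or about 90 per arm after ineligible patients and non-starters are removed. If the 48% share holds, 75 per arm needs an evaluable share of 150/(515 × 0.48) = 61%, and 60 per arm needs 120/(515 × 0.48) = 49%, unless the losses occur after radiotherapy starts.

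**7. With the 1-year look.** The plan expects 90% at 1 year and uses 85% as its 2-year reference, so 10 of 15 percentage points of failure, two-thirds, fall in year 1. Applied to a true 75% arm, the year-1 rate is 0.25 × 2/3 = 0.167. The review is then triggered with probability 0.68, and the arm passes at the end without a review with probability 0.14. Under a constant hazard the year-1 rate is 1 − √0.75 = 0.134, and these become 0.45 and 0.19.

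**The case for a change.** The strongest case for change is that the omission is selective. The plan prints operating characteristics for the interim look, the exploratory arm comparisons and the quality-of-life comparison, but not for its main efficacy decision. A true 75% arm passes about one time in four, and nothing shows whether that was intended. The arm comparison would not settle it, since its stated power is 0.32 for 85% against 75%. The interim trigger leads to a review, not a failure. Writing down a floor would cost little and, with a lower-limit rule, a shortfall in patients would cost power instead of weakening the screen.

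The omission is real, and so is the direction of the dependence on n. Neither shows that the rule is wrong. The interval table already contains the smallest passing result with its lower limit of 0.71, so a reader can see what a bare pass looks like, though not as an error rate. Any floor would have to be supplied from outside the documents: 70% changes nothing at 90 per arm, and 75% lowers the chance of keeping a true 85% arm from 96% to 73%. Which error to protect when patients are lost is also a choice: at n = 60 a 70% lower-limit rule passes a true 85% arm 82% of the time, against 97% under the plan's rule.

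Pre-radiotherapy drop-out cannot be used to argue for a shortfall below 90, because the accrual target already removes it. Retrospective pathology review could take out some further patients, but no loss rate is given, and sizes of 75 or 60 per arm are a stress range.

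**Conclusion.** No change to the plan is needed. At the planned size the upper-limit rule is a cut-off of 71/90: it passes a true 70% arm 3.9% of the time and a true 85% arm 96% of the time, which is reasonable for a phase II screen meant not to discard a good regimen. The obvious replacement gives the same cut-off, and a stricter one only exchanges one error for the other. Down to 80 per arm the pass probability at a true 70% stays at or below 7.7%. The 1-year look adds protection with printed operating characteristics.

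What remains is missing detail: the plan does not say that 71/90 is the cut-off, which 2-year rate it means to screen out, or how often an arm would pass. Analysts can derive the cut-off and the pass probabilities from the stated rule and size, and a line beside the interval table would record them. The conclusion rests on about 90 analysable patients per arm, as the plan expects, and on the exact interval it specifies. The 70% and 75% floors are illustrations, and the interim figures depend on the assumed split of events between years 1 and 2.

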RTOG 0129 was a phase III trial that compared standard and accelerated boost RT regimens, both with concurrent cisplatin. There were no differences in efficacy between the two arms. A retrospective analysis of the patients enrolled in RTOG 0129 has been published. This analysis combined cases of OPSCC in both arms of the trial ( $n=317$ ) and demonstrated that tumor positivity for HPV-16 was associated with HR for death of 0.36 ( $p=0.0001$ ). Patients with HPV-negative OPSCC cancer had essentially identical progression-free survival as those with hypopharynx and larynx primaries, with an approximate 60% 1-year rate. Smoking history modified the risk of relapse in the RTOG 0129 analysis. OPSCC patients who were HPV-positive but smoked 20 pack-years or more had a HR for OS of 1.91 (95% CI, 1.20-3.05) over patients who were HPV positive but smoked less than 20 pack-years; patients who were HPV-negative and smoked less than 20 pack-years had a HR of 2.25 (1.44-3.50) and patients who were HPV-negative but smoked 20 pack-years or more had a HR 4.30 (2.40-7.71); and the 2-year PFS was 95%, 80%, 71% and 63%, respectively. Within the HPV-positive group, patients could be further divided by tobacco use history (in pack-years, = 10 vs. >10) and N stage (N0-2a vs. N2b-3). Patients with > 10 pack-years and N2b-3 disease make up the intermediate risk group; all others comprise the low-risk group. Looking into smoking history further, patients who were p16+ and smoked >5 pack-years can be categorized as “unfavorable” or “intermediate risk”: with a 2-year PFS of 65% and a 3-year PFS of 61% using CRT in RTOG 0129. Therefore, a smoking history of 5 pack-years has been proposed as the cut-off to define favorable vs. unfavorable HPV-positive OPSCC (essentially using p16 immunoreactivity as a surrogate marker for HPV infection).

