4.2.4.2 Stratification Factors - Intermediate Risk

- Smoking Status: ≤ 10pk-yr vs. >10pk-yr

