In the primary QOL analysis, we plan to combine the post-operative RT arms (B & C) and compare to patients selected for post-operative chemoRT (arm D), which would be expected to have toxicity similar to, but less severe than, a primary CRT approach. This comparison is most similar to the setting of a possible future phase III trial. From a prior trial of CRT approach, about 25% of the patients had improved FACT-H&N from baseline to 6 months, 25% were stable, and 50% worsened, which is expected to be similar to, or slightly worse than the experience of arm D in this phase II trial. Given the more severe overall toxicity and probable greater late toxicity associated with the use of both radiation and chemotherapy, we hypothesize that a higher proportion of patients in arm B/C will have recovered their FACT-H&N scores to baseline level or higher at 6 months, and we consider a difference, or Delta, of 10% (Arms B/C vs. Arm D) to be important outcome. Comparison between Arm B and Arm C (in mean score change and/or proportion of patients with improved/stable score at 6 months) is also important endpoint but this will be only exploratory. Any comparison results will be interpreted with caution. Descriptive statistics will be provided for FACT-H&N and MDASI-HN at various measurement points.

The table below shows the power of detecting various Delta value (Arms B/C vs. D) under various compliance rate (the proportion of patients who complete PRO surveys at both baseline and 6 months post-RT visits), using a one-sided Fisher's exact test with type I error rate of 0.10, assuming 48% intermediate risk patients and 32% high risk patients among evaluable patients.

Compliance Rate	No. of analyzable pts (Arms B/C vs. Arm D)	Delta (Arms B/C vs. D)		
		10% (65% vs. 55%)	15% (70% vs. 55%)	20% (75% vs. 55%)
40%	120 (72 vs. 48)	0.35	0.58	0.79
60%	180 (108 vs. 72)	0.46	0.73	0.91
80%	240 (144 vs. 96)	0.56	0.83	0.96

One of the randomized arms is likely to be selected for a future phase III study. Although the QOL endpoint is not built into the primary selection criteria, in case that the efficacy outcomes for the two randomized arms are similar, the 50Gy schedule will be considered in the phase III study with the expectation that QOL will also be better in this arm, unless there is evidence otherwise.

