#### 9.8 Randomization Scheme

Patients enrolled into this study will be assigned to one of the four treatment arms after transoral surgery based on their histologic risk status. Patients with low-risk will be assigned to the observation group (Arm A). Patients with intermediate-risk will be randomized (with a 1:1 allocation ratio) into either Arm B (IMRT 50 Gy) or Arm C (IMRT 60 Gy). Patients with high-risk will receive post surgery concurrent cisplatin and IMRT 66 Gy (Arm D). The method of permuted blocks will be used for randomization with current/former smoking history ( $\leq 10$  vs.  $> 10$  pack-years) as stratification factor.

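### For the exploratory 50 Gy versus 60 Gy comparison, section 9.3 names only an unstratified Fisher test and plans no interval for the difference; a smoking-stratified test with a 95% CI would serve better (minor)

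*Combined protocol and SAP*

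**What the plan says.** - **Status of the comparison.** Section 9.3 lists B vs C, B vs D and C vs D as exploratory. It then says that "the exploratory comparison of 2-year PFS rate between the two randomized arms is more important", because one of the two arms is likely to be carried into phase III, and sets p ≤ 0.05 for it.
- **Test.** No analysis test is prescribed for B vs C. The only one named is the assumption under the power table: a two-sided Fisher's "exact test and 90 analyzable patients in Arms B or C, and 120 analyzable patients in arm D". The stated power for C vs B is 0.32, 0.62, 0.85 and 0.96 for 85% against 75%, 70%, 65% and 60%.
- **Intervals.** "In analyzing the 2-year PFS rate, 90% exact binomial confidence intervals will be computed for each arm". None is described for the difference between arms.
- **Randomisation.** Section 4.2.4.2 gives the intermediate-risk stratification factor as "Smoking Status: ≤ 10pk-yr vs. >10pk-yr". Section 9.8 agrees: "The method of permuted blocks will be used for randomization with current/former smoking history" as the factor. No PFS analysis in section 9 uses it.
- **Use of the result.** Section 9.5 says that "in case that the efficacy outcomes for the two randomized arms are similar, the 50Gy schedule will be considered in the phase III study". It does not define *similar*.

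**The concern.** This is the only randomised contrast in the trial, and the plan links it to the choice of dose for the next study. Three features weaken what it can deliver.

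- The named test leaves about a third of its nominal 5% error rate unused.
- A factor thought prognostic enough to stratify the randomisation is left out of the analysis.
- The plan gives the reader a p-value and two separate per-arm intervals, but no direct statement of how large a loss from 50 Gy remains compatible with the data.

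The third feature carries the most weight. Section 9.5 leans towards 50 Gy when efficacy looks similar. With power of 0.32 against a 10-point loss, a non-significant p-value is the likely result even when such a loss is real.

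**Working it through.** **Inputs from the plan.** 90 analysable patients per arm; two-sided α = 0.05; reference 2-year PFS 85%; alternatives 75, 70, 65 and 60% (section 9.3); 1:1 allocation with smoking strata (section 9.8).

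**Inputs not in the plan (assumed).** The share of patients with ≤ 10 pack-years is taken as 50-80%, and the odds ratio for being event-free, light against heavy smokers, as 1 to 4.75. The top value comes from section 1.3, where an earlier chemoradiation trial reports that "2-year PFS was 95%, 80%, 71% and 63%, respectively" for its HPV and smoking groups. The two HPV-positive figures give (0.95/0.05)/(0.80/0.20) = 19/4 = 4.75. That contrast is at 20 pack-years, not 10, so it is only a guide.

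**Step 1: reproduce the plan.** Enumerate every pair (x, y) of event-free counts out of 90. Reject where the two-sided Fisher p ≤ 0.05. Power is the sum over the rejection region of Bin(x; 90, p₁) × Bin(y; 90, p₂). This gives 0.323, 0.618, 0.848 and 0.959, which matches all four stated values.

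**Step 2: true size of Fisher.** The same sum with p₁ = p₂ gives 3.4, 3.2, 3.1 and 3.0% at a common PFS of 75, 80, 85 and 90%.

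**Step 3: stratified alternative.** In stratum s with n_s patients per arm, a_s event-free in one arm and m_s event-free in both together, the uncorrected CMH statistic is

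[Σ(a_s − m_s/2)]² / Σ{ n_s² m_s (2n_s − m_s) / [(2n_s)² (2n_s − 1)] },

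rejecting at 3.841 or more. Marginal rates are held at the plan's values.

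| Difference | Fisher | CMH, no smoking effect | CMH, over the assumed range |
|---|---|---|---|
| 10 points | 0.32 | 0.39 | 0.39-0.42 |
| 15 points | 0.62 | 0.68 | 0.68-0.73 |
| 20 points | 0.85 | 0.88 | 0.88-0.92 |
| 25 points | 0.96 | 0.97 | 0.97-0.98 |

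The size of the CMH test is 4.8-5.1%.

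**Step 4: where the gain comes from.** The unstratified, uncorrected Pearson test has power 0.387 at 10 points. So 0.387 − 0.323 = 0.064, about 6 points, comes from dropping Fisher's conservatism. The stratum adds 0 to 4 points on top. A continuity-corrected CMH test would give back most of the gain, with power of only 0.32-0.35 at 10 points.

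**Step 5: effect on the threshold.** With 77/90 event-free in Arm C, Fisher first reaches p ≤ 0.05 when Arm B has 65/90 (p = 0.044), a shortfall of 12/90 = 13.3 points. The uncorrected unstratified test gets there at 66/90 (p = 0.042, against 0.064 by Fisher), a shortfall of 11/90 = 12.2 points.

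**Step 6: the interval.** With 77/90 in both arms the observed difference is zero. A simple 95% half-width is 1.96 × √(2 × 0.856 × 0.144/90) = 0.103. The Newcombe half-width is 10.5 points unstratified and 10.3-10.4 stratified. With 77/90 against 67/90, an 11.1-point shortfall, Fisher gives p = 0.093, yet the unstratified Newcombe 95% interval for B − C runs from −22.6 to +0.6 points.

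**The case against.** The other side has a good deal right. The comparison is labelled exploratory, and the primary decision is the per-arm exact interval. Fisher is valid, its error lies on the safe side, and the power column is correct. Fisher appears only as a power assumption, so the plan is silent on the analysis test and does not mandate an unstratified one. Choosing between an exact and an uncorrected test at this sample size is partly taste, and it moves the significance threshold by one patient. The smoking inputs are assumed, and with no smoking effect the stratum adds nothing. Stratifying barely narrows the interval. All of this stands, and it keeps the point minor.

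Three stronger readings are tempting, and the documents support none of them.

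- *A reader might infer that the named test inflates false positives or that the power table is wrong.* Steps 1 and 2 show the reverse.
- *A reader might infer that ignoring the stratum is the main loss.* Most of the gain comes from the less conservative test.
- *A reader might infer that p > 0.05 triggers selection of 50 Gy.* Section 9.5 ties no rule to the p-value. It says only that this schedule will be considered, subject to contrary evidence.

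One objection does not remove the point: that anyone can compute a difference interval from the per-arm counts. That holds only for the unstratified interval, and it does nothing to stop non-significance from being read as similarity.

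**Conclusion.** The concern holds as a gap in efficiency and reporting for an exploratory comparison, not as an error. The gain in power is modest: about 6 points from the less conservative test, plus 0 to 4 from the stratum, at a 10-point difference. Power of about 0.4 is still low, and no choice of test cures a limit set by sample size. The missing interval is the more useful part, because with equal observed results the data would still be compatible with a loss of about 10 points. The Fisher figures, the no-smoking-effect CMH figures and the unstratified intervals rest only on the plan's inputs and illustrative counts. Any CMH power above 0.39, 0.68, 0.88 and 0.97 rests on the assumed smoking share and effect.

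**What to change.** In section 9.3:

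- Name the B vs C analysis, restricted to the randomised intermediate-risk patients: a CMH test stratified by smoking (≤ 10 vs > 10 pack-years), without continuity correction.
- Report the stratum-weighted difference in 2-year PFS with a 95% CI, for example a stratified Newcombe interval.
- Say that any statement under section 9.5 that the arms are similar will rest on that interval and not on a non-significant p-value.
- Leave the Fisher power column as a conservative figure. If it is restated, give 0.39, 0.68, 0.88 and 0.97 as the floor and label anything higher as dependent on assumed smoking inputs.
- State the trade-off: Fisher's guaranteed size is exchanged for a size of about 5% (4.8-5.1%). The sentence on the family-wise rate of 0.10 should then be worded as approximate.

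The cost is a few sentences. Smoking status is already a stratification factor at Step 2. The sample size, the data collected and the primary per-arm 90% exact interval rule do not change.
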